6.5.3	Visit 3: Week 2 (\pm 2 days)	25
6.5.4	Visit 4: Week 4 (\pm 2 days)	25
6.5.5	Visit 5: Week 6 (\pm 2 days)	26
6.5.6	Visit 6: Week 8 (\pm 2 days)	26
6.5.7	Visit 7: Week 10 (\pm 2 days)	26
7	STATISTICAL PLAN	26
7.1	SAMPLE SIZE DETERMINATION	26
7.2	STATISTICAL METHODS	27
7.3	SUBJECT POPULATION(S) FOR ANALYSIS	27
8	SAFETY AND ADVERSE EVENTS	27
8.1	ADVERSE EVENT DEFINITIONS	27
8.2	CLASSIFICATION OF ADVERSE EVENTS BY SEVERITY	28
8.3	CLASSIFICATION OF ADVERSE EVENTS BY RELATIONSHIP TO STUDY TREATMENT	28
8.4	ACTION(S) TAKEN	29
8.5	OUTCOME	29
8.6	ADVERSE EVENT REPORTING	29
8.7	SERIOUS ADVERSE EVENT REPORTING	29
8.8	IN CASE OF AN EMERGENCY	30
8.9	DATA SAFETY MANAGEMENT PLAN	30
8.10	STUDY OVERSIGHT	30
9	CONFIDENTIALITY	31
10	SOURCE DOCUMENTS	31
10.1	RECORDS RETENTION	31
11	ETHICAL CONSIDERATIONS	31
12	STUDY FINANCES	32
12.1	FUNDING SOURCE	32
12.2	CONFLICT OF INTEREST	32
12.3	SUBJECT STIPENDS OR PAYMENTS	32
13	REFERENCES	33

SCHEDULE OF VISITS AND PROCEDURES

	Screening	Day 1 (Pre-Dose)	Day 1 (Post-Dose)	Week 2	Week 4	Week 6	Week 8	Week 10
Informed Consent	X							
Demographic Information	X							
Medical History/Con Meds	X							
Ophthalmic/Dry Eye History	X							
Vital Signs		X		X	X	X	X	X
Ophthalmic Examination (Slit lamp)	X	X		X	X	X	X	X
Ocular surface redness score	X	X		X	X	X	X	X
Schirmer 1 test and Rose Bengal staining	X						X	
Pregnancy Test (urine)*	X							
Best Spectacle Corrected Visual Acuity		X						X
Randomization visit		X						
First Study Medication		X						
Drug dispensation visits			X	X	X	X		
Instruction on study medication self-administration			X					
Ocular Surface Disease Index (OSDI)		X		X	X	X	X	X
Visual Analogue Scale (VAS)			X	X	X	X	X	
Physical inspection of nose & oropharynx				X	X	X	X	X
Clinical Global Impression (CGI)		X		X	X	X	X	X
Subject Global Assessment (SGI)		X		X	X	X	X	X
Adverse Events/ Concomitant Medications		X	X ⁺⁺	X	X	X	X	X

*If applicable ++ AEs only

ABBREVIATIONS

AE	Adverse Event
APC	Antigen-presenting cells
BSCVA	Best Spectacle Corrected Visual Acuity
EC	Ethics Committee
eDNA	Extracellular DNA
CNL	Corneal Neurobiology Laboratory
CRF	Case Report Form
CGI	Clinical Global Impression
DCF	Data Clarification Form
DED	Dry Eye Disease
DNase I	Deoxyribonuclease I
FDA	Food and Drug Administration
FVC	Forced vital capacity
GCP	Good Clinical Practice
ICH	International Conference on Harmonization
IB	Investigator's Brochure
IOP	Intraocular pressure
IRB	Institutional Review Board
KCS	Keratoconjunctivitis sicca

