3.2.4 Efficacy End Point: Ocular surface Rose Bengal dye staining score

Ocular surface staining will be assessed using Rose Bengal dye. Saline moistened 1% Rose Bengal dye impregnated strips will be used to instill the dye on the inferior palpebral conjunctiva and scoring of corneal and conjunctival staining will be performed by a slit lamp examination after 15 seconds using the grading system described by the 1995 NEI workshop.³⁰ Corneal staining will be graded in 5 zones

and conjunctival staining will be graded in 6 zones. Each zone will be graded from 0 to 3 based on the density of punctate staining. The final staining score will be the sum of individual scores from all 11 zones (5 corneal, 6 conjunctival). The scoring pattern is represented below.

[figure not shown]
Complete ocular surface staining clearance means absence of any punctate or confluent staining with Rose Bengal dye defined as Rose Bengal staining score of 0.

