3.3 Secondary Endpoints

The secondary study endpoints will include:

1. Change in tear secretion as measured by Schirmer I test
2. The proportion of eyes achieving complete ocular surface staining clearance after treatment
3. Visual acuity change
4. Change in frequency of administration of artificial tears or concomitant eye drops
5. Change in number of corneal filaments (slit-lamp examination)

Corneal filaments are mucous tags that are adherent to the surface of cornea. The number of such mucus tags will be counted on each clinical examination (slit-lamp examination).

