4.1 Inclusion Criteria

Patients will be eligible for the study if all of the following criteria are met:

1. Aged 18 years or older.
2. Capable of giving informed consent and does provide informed consent.
3. Documented Dry Eye Disease for at least 6 months.
4. Schirmer I <10
5. Corneal/ conjunctival (Rose Bengal) staining ≥ 1
6. Ocular symptoms must be considered as annoying or activity limiting (OSDI ≥ 13 ; mild).
7. Women must be post-menopausal ≥ 1 year, or surgically sterilized. If not, a negative urine pregnancy test is required within 14 days of receiving her first dose of test medication (placebo/ study drug) along with definite evidence of contraceptive use during the duration of the study. Women of reproductive age should use a method of birth control that is acceptable to the subject and the study doctor. This may include oral contraceptive pills, birth control implants, barrier methods or abstinence. If a subject mentions she suspects she may be pregnant after being enrolled, another pregnancy test will be administered. If the test is positive, she will be discontinued from the study immediately.

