7.2 Statistical Methods

Descriptive statistics will be used for all primary and secondary endpoints, when appropriate.

We will define outcome measures on the basis of the change for each subject from baseline to each follow-up point, controlling for chance imbalances in the mean baseline values between treatment groups. A Wilcoxon Signed-rank test will be used for paired comparison of quantitative variables (OSDI score) between the baseline and each post-baseline time points. Chi-square test will be used to compare qualitative variables (Investigator's rating scale/ changes in concomitant medications) between the 2 groups. Two-sided $P < .05$ will be considered statistically significant for all comparisons. 95% Confidence interval will be provided for comparison between the investigational drug and placebo for the primary efficacy, the primary safety, and the secondary endpoints.

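### Section 7.2 gives no method that carries its stated baseline control to the yes/no staining-clearance endpoint, so some precision may be lost (minor)

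*Combined protocol and SAP*

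**What the plan says.** - **Score.** Section 3.2.4: "Each zone will be graded from 0 to 3 based on the density of punctate staining", and "The final staining score will be the sum of individual scores from all 11 zones". Complete clearance is "defined as Rose Bengal staining score of 0", whatever the starting score.
- **Entry.** Section 4.1 requires "Corneal/ conjunctival (Rose Bengal) staining ≥ 1". It sets no upper limit and does not say which eye must qualify.
- **Endpoint.** Section 3.3, item 2, is "The proportion of eyes achieving complete ocular surface staining clearance after treatment". It counts eyes, and Section 6.5 has both eyes examined.
- **Timing.** The Schedule of Visits has a row "Schirmer 1 test and Rose Bengal staining", marked at Screening and Week 8. A pre-treatment score is therefore already collected.
- **Allocation.** Section 5.3 describes 72 random draws of group 1 or 2, with no blocks and no strata.
- **Analysis.** Section 7.2 defines outcomes by change from baseline and expresses a general aim of controlling for random baseline differences between the arms. It names no model, covariate or strata. It then says: "Chi-square test will be used to compare qualitative variables". The bracketed examples are the investigator's rating and changes in concomitant medication, not clearance. It also promises a 95% confidence interval for drug against placebo on the secondary endpoints.

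**The concern.** Clearance is an absolute end state. An eye that enters at 1 clears by losing one grade in one zone, while an eye that enters at 20 must lose 20 points. The endpoint counts both alike. If entry staining predicts clearance, two things follow. A chance difference in entry severity between the arms, which nothing in the allocation limits, feeds into the observed clearance difference. And an unadjusted test leaves explainable variation in the error term.

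Section 7.2 shows that the authors want baseline control, but the one test it names for qualitative outcomes cannot provide it. At stake is the precision of one secondary endpoint in a small trial that will be read for signals of efficacy.

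**Working it through.** **The plan's own figure.** There is none to reproduce. Section 7.1 gives a target of 30 completers per arm, and the documents state no clearance rate, effect size or power for any endpoint.

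**Range.** 11 zones × 3 = 33, and entry needs at least 1, so the qualifying score runs from 1 to 33. A fellow eye could start at 0, because 4.1 does not require both eyes to qualify.

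**Inputs from the documents.** 30 per arm (7.1); two-sided 0.05 (7.2); no stratification (5.3).

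**Assumed inputs, since the documents give none.** One outcome per subject. Baseline score lognormal within 1–33, median 5, log-SD 0.8. Vehicle clearance about 17–19%. logit P(clear) = a − b·log(baseline) + logOR·drug, with logOR 1.2, 1.6 and 2.0. In the b = 1.5 and 2.5 settings, true drug clearance is then about 31–52%.

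**Tests compared.**
- Chi-square without continuity correction: z = (p₁ − p₀)/√(2p̄(1 − p̄)/30).
- Cochran-Mantel-Haenszel (CMH) over baseline tertiles: [Σ(aₖ − n₁ₖm₁ₖ/Nₖ)]² / Σ[n₁ₖn₀ₖm₁ₖm₀ₖ/(Nₖ²(Nₖ − 1))]. In tertile k, aₖ is drug-arm clearers, n₁ₖ and n₀ₖ the arm sizes, m₁ₖ and m₀ₖ the numbers clearing and not clearing, and Nₖ the total.

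**Power (%) at logOR 1.2 / 1.6 / 2.0** (1,500 to 3,000 simulated trials per setting)

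| Slope b | Fall in odds of clearance per doubling of baseline (2^b) | Chi-square | CMH |
|---|---|---|---|
| 0 | none | – | about 1 point lower |
| 0.5 | 1.4-fold | 52 / 80 / 94 | 52 / 80 / 94 |
| 0.9 | 1.9-fold | 45 / 74 / 90 | 47 / 75 / 91 |
| 1.5 | 2.8-fold | 33.9 / 59.3 / 80.6 | 40.0 / 66.9 / 86.5 |
| 2.5 | 5.7-fold | 23.1 / 38.3 / 56.6 | 29.1 / 48.5 / 70.1 |

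A repeat of the last two rows gave 36/62/81 against 40/66/86 and 23/39/58 against 28/49/71. Gains in single cells of those rows therefore lie between 4 and 14 points, and about 5 to 12 is a fair summary given simulation error. With 1,500 trials, the standard error of a power near 50% is √(0.25/1500) = 1.3 points.

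**Type I error.** For b = 1.5 and 2.5: chi-square 5.7% and 5.1%; CMH 5.1% and 4.7%.

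**Effect of chance imbalance.** The SD of the between-arm difference in mean log baseline is about 0.8 × √(2/30) = 0.21 before truncation to 1–33, and about 0.20 in the simulation. One such SD moves the clearance difference by about 4 to 6 points at b = 1.5 and 2.5.

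**Second method.** Logistic regression on log₂ baseline was compared with the unadjusted chi-square at true clearance of 20% against 50%, for three baseline distributions (uniform 1–33, skewed with mean about 7, narrow 4–12).
- Unadjusted power is 0.692 by formula.
- Adjustment added about 2 points (0.688 to 0.704: narrow range, 1.5-fold fall per doubling) to 19 points (0.688 to 0.877: uniform range, 4-fold fall). This is slightly flattering, because the adjusted test rejected 5.0–6.6% of the time under the null.
- When the drug arm happened to be milder by more than 0.3 SD (about 12–14% of trials), the mean observed difference was 0.32–0.42. When it was worse by that much, the mean was 0.19–0.27. The true difference is 0.30.

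**The case against.** Four stronger readings are tempting, and the documents do not support them.

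1. **That the plan ignores baseline.** It does not. Section 7.2 states a general aim of baseline control and exempts no endpoint. What is missing is a method that delivers it for a yes/no outcome.
2. **That 7.2 prescribes a chi-square for clearance.** Clearance is not among its examples, so this is an inference. It is a reasonable one, because no other between-group test is named for qualitative variables and a confidence interval against placebo is promised for secondary endpoints.
3. **That the result would be biased or the test invalid.** Randomization keeps overall type I error near 5%. Dependence on the entry mix is sampling variation, which the confidence interval already reflects.
4. **That a large power loss is established.** Nothing in the documents shows how strongly entry staining predicts clearance. With weak dependence the gain from stratifying is nil to 2 points, and with none it is a small loss.

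Two further points stand. Clearance is one of five secondary endpoints in a Phase I/II trial, and mean staining reduction is already a primary endpoint in 3.2, so graded information is not lost. Stratifying can also leave thin cells. In simulations of the strongest dependence with a drug effect, a tertile with no clearers occurred in 42–65% of trials in one run and 27–48% in another. These points lower the grade of the concern, but they do not remove the gap in 7.2.

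**Conclusion.** The point holds as a minor one about precision and specification. Section 7.2 announces baseline control and does not say how it reaches staining clearance, although the entry score may lie anywhere from 1 to 33 and allocation is unstratified. The unadjusted comparison would be valid. With 30 subjects per arm and one outcome per subject, tertile stratification changes power by about -1 point with no dependence on baseline, 0 to 2 points with weak dependence (odds falling up to 1.9-fold per doubling), and about 5 to 12 points with moderate to strong dependence (2.8- to 5.7-fold). These figures rest on the assumed baseline distribution, clearance rates and slopes. The documents do not show which row of the table applies.

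**What to change.** In Section 7.2, add that staining clearance will be compared between arms adjusting for the Screening Rose Bengal score, by a Cochran-Mantel-Haenszel comparison. Specifically:

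- Fix the strata from the pooled, blinded distribution of Screening scores: tertiles, or two strata if clearers are sparse, with the rule written down before unblinding.
- Report the stratified risk difference with its 95% CI, and keep the crude proportions as description.
- Use one clearance outcome per subject, or a method that accounts for two eyes per subject. State how an eye scoring 0 at Screening is counted.

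**Cost.** Wording only; the score is already collected. The choice between a per-subject outcome and a two-eye method has to be made as well, because 3.3 counts eyes. Some strata may contain no clearers. Such a stratum adds nothing to the test, but does not invalidate it. If baseline staining turns out not to predict clearance, about 1 point of power is lost.

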3.4 Primary Safety Endpoints

Safety assessments include Vital Signs, recording of all complications and adverse events, as well as ophthalmic exam findings. All ocular and non-ocular adverse events will be assessed for severity and relationship to the investigational product.

Primary safety endpoint:

- The proportion of subjects at week 8 who were able to successfully complete a full eight weeks of therapy with topical administration four times per day (q.i.d.)

Secondary safety endpoint:

- All adverse events reported, whether deemed related to treatment, or not.
- Clinically significant changes in vital signs or ophthalmic examination from baseline.

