1.5 Dose Rationale and Risk/Benefits

RhDNase1 1mg/ml (0.1%) will be applied topically to the ocular surface as eye drops. This is the same dose as is currently in use in patients with Cystic Fibrosis. The drug formulation is being used unchanged. This dose has been effective in reducing eDNA content when given to patients with cystic fibrosis. We do not expect any serious adverse events with this dose.

Drugs are routinely applied topically to the ocular surface as eye drops because of easy access to the ocular tissues and good drug bioavailability. Therefore, we will use rhDNase1 topically. We have chosen an eight week duration of therapy because we expect rhDNase1 to be used continually; eight weeks of treatment will give us better data to predict side effects during long-term use. Since rhDNase1 is not expected to increase the production of natural DNase I, but rather it only supplements it so that the imbalance of decreased tear fluid DNase I is corrected, we expect long-term use of rhDNase1.

RhDNase is currently used as an inhaled drug in adults and children with cystic fibrosis. Patients with cystic fibrosis have experienced a change in or loss of their voice, discomfort in the throat, chest pain, red watery eyes, rash, dizziness, fever, or runny nose. Most of these are systemic side-effects that are not generally seen with eye drops. These side effects are usually mild and short-lived.

The most likely discomforts a subject may experience by having RhDNase administered as eye drops are eye burning or irritation, red watery eyes, or feeling like there is something in the eye. To see how subjects react to the study medication, their first dose will be given by the investigator in the clinic itself. Afterwards subjects will be asked to rate tolerability of the drug on the Visual Analogue Scale. Also, at each) visit, subjects will be asked to complete the Visual Analogue Scale.

An allergic reaction to the drug cannot be predicted beforehand. In event of an allergic reaction, the drug will be stopped immediately, and symptoms will be managed appropriately depending on the severity of the reaction.

Restasis, a drug used to treat DED, is held during the 14 day wash-out period and over the entire course of the study. Holding Restasis may increase the subject's risk of worsening DED.

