Participants randomized to the placebo have a risk of worsening dry eye disease. All study subjects will be encouraged to contact the research team immediately if they experience worsening of their DED.

No psychological, social, legal, or financial risk is expected from participating in the research.

There is always a risk of a loss of confidentiality.

2 Study Objectives

The objective of this study is to establish whether patients with Dry Eye Disease are able to tolerate receiving rhDNase1 0.1% eye drops four times a day for eight weeks (primary tolerability objective) and to investigate the preliminary efficacy of rhDNase1 topical eye drop solution 0.1% in treating Dry Eye Disease (primary efficacy objective).

3 Study Design

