5.7 Rescue Plan

The research staff, including the PI, will be masked to randomization, thus will not be aware if a particular subject receives study drug or placebo. Subjects will be monitored by the Principal Investigator at each study visit. Any worsening of DED or any adverse event (AEs) will be recorded and in the case of AEs followed to resolution. In case of clinical worsening/ adverse event(s), based on the individual subject's clinical condition, one or more of the following therapeutic decisions may be implemented:

- (1) Increasing the frequency of artificial tears use,
- (2) Re-starting the use of anti-inflammatory therapy (Restasis/ corticosteroids),
- (3) Discontinue the study drug.

The decision will be made by the Principal Investigator based on his clinical judgment and the individual subject's clinical condition. If additional anti-inflammatory therapy (Restasis/ corticosteroids) is instituted and/or the study drug is discontinued, the subject will be withdrawn from the study. If an adverse event is severe enough to discontinue the subject from the study, the PI may decide to break the subject's randomization code if it seems relevant to the treatment of his/her ocular condition at that time. He/ She will receive the treatment required for his/ her eye condition as per established clinical guidelines.

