8.4 Action(s) Taken

One or more of the following will be recorded by the Investigator for each adverse event:

- No action taken
- Discontinued study drug (Subject withdrawn due to this adverse event)
- Administered therapy
- Hospitalized subject (due to this adverse event)
- Other (specify) - includes tests, labs confirming reaction

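### The primary safety endpoint pools stops for intolerance with withdrawals for worsening dry eye, so a vehicle excess of worsening could understate drug intolerance in the arm comparison

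*Combined protocol and SAP*

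**What the plan says.** - **Objective (section 2).** The tolerability objective asks whether patients can tolerate the drops four times a day for eight weeks.
- **Endpoint (3.4, repeated in the Study Summary).** The share of subjects, assessed at week 8, "who were able to successfully complete a full eight weeks of therapy", on the four-times-daily regimen. No reason for failure is distinguished, and successful completion is not defined further.
- **Analysis (7.2).** "95% Confidence interval will be provided for comparison between the investigational drug and placebo for the primary efficacy, the primary safety" and the secondary endpoints. Two-sided P below .05 "will be considered statistically significant for all comparisons".
- **Analysis population (7.3).** At least two weeks of treatment and attendance at the week 2 visit are required.
- **Withdrawal (5.7).** For clinical worsening or an adverse event in either arm: "If additional anti-inflammatory therapy (Restasis/ corticosteroids) is instituted and/or the study drug is discontinued, the subject will be withdrawn from the study". Section 5.6 has a parallel rule that speaks of exclusion from the study; I read it as withdrawal, in line with 5.7.
- **Anticipated problems (1.5).** "Participants randomized to the placebo have a risk of worsening dry eye disease". The likeliest discomforts of the drug "are eye burning or irritation, red watery eyes, or feeling like there is something in the eye".
- **Recording of cause (8.4, 8.5).** The adverse event form has an entry "Discontinued study drug (Subject withdrawn due to this adverse event") and a flag for events that caused withdrawal. No endpoint or analysis uses either.

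**The concern.** Completion answers a different question from tolerance. A subject can fail to complete because the drops are uncomfortable, because the dry eye gets worse and rescue is started, or for an unrelated reason. The first cause would be expected mainly on drug. The second would be more frequent on vehicle if the drug works. In the arm comparison these two causes act in opposite directions, so a gain in efficacy improves the safety result with no gain in tolerability.

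At stake is how the primary safety result is read. Equal completion could be reported as equal tolerability when more drug subjects had stopped because of the drops. Section 1.4 says that there is no published report of this drug used as eye drops, so outside data would not correct the impression.

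**Working it through.** **The plan's own figures.** Section 7.1 gives 72 enrolled and 20% non-completion from all causes, not split by arm or reason. That is 72 × 0.20 = 14.4 non-completers. (The remaining 57.6, or 28.8 per arm, falls short of the intended 30; that is a separate matter and nothing below depends on it.) I use 72 / 2 = 36 per arm. This is the expected split under the simple randomisation in 5.3, not a guaranteed one. The plan states no power, safety margin or cause-specific rate, so there is no planned figure to reproduce.

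**Direction.** Let i be the proportion stopping for intolerance and w the proportion withdrawn for worsening, with D for drug and V for vehicle, and other stops equal in the two arms. Then

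completion difference (D − V) = (w_V − w_D) − (i_D − i_V).

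Intolerance is reported faithfully only if w_V = w_D. Any vehicle excess of worsening is subtracted from it.

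**Size under assumed rates.** Fix i_D = 15%, w_D = 3%, i_V = 3%, and set other stops to zero. Drug non-completion is 15 + 3 = 18%, and vehicle non-completion is 3% + w_V. The true intolerance difference is 15 − 3 = 12 points throughout. With X_D ~ Bin(36, 0.18) and X_V ~ Bin(36, 0.03 + w_V), the chance that drug completion is at least as high as vehicle completion is P(X_D ≤ X_V), by exact enumeration:

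| Vehicle worsening w_V | Vehicle non-completion | True completion difference (D − V) | P(drug looks as good or better) |
|---|---|---|---|
| 3% | 6% | −12 points | 8% |
| 5% | 8% | −10 points | 13% |
| 8% | 11% | −7 points | 25% |
| 10% | 13% | −5 points | 34% |
| 15% | 18% | 0 | 56% |

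The last row is full cancellation: true completion is equal, and 56% is one half plus half the chance of a tie.

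**What a cause-specific comparison gains.** At 15% versus 3% intolerance, the drug arm has the higher observed intolerance rate in 95% of trials, but that counts direction only. The Newcombe 95% CI for the intolerance difference excludes zero in 36% of trials (Fisher P below .05 in 23%). For all-cause completion, the same CI excludes zero against the drug in 32% when worsening is 3% in both arms (18% versus 6% non-completion), and in about 2% when vehicle worsening is 15% (18% versus 18%). So the breakdown adds little when nothing cancels, and it keeps its sensitivity when something does.

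**Illustrative counts (assumed).** On drug, 5 of 36 stop for intolerance and 2 for other reasons. On vehicle, 5 of 36 are withdrawn for worsening and 2 for other reasons.

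- Completion: 29/36 versus 29/36, difference 0 (Newcombe 95% CI −18 to +18 points).
- Stops for intolerance: 5/36 versus 0/36, difference 5/36 = 13.9 points (95% CI +1.5 to +28.7; Fisher P = 0.054).

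**Timing.** These sums count every subject dosed. Under 7.3, a subject who stops before two weeks, or misses the week 2 visit, leaves the analysis population and may not be counted at all. That could remove early intolerance stops.

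**The case against.** **Does the plan expect worsening on vehicle?** A reader might infer this from 1.5, but that section names only a risk. Section 5.6 says that no significant clinical worsening is expected, because artificial tears continue. Cyclosporine and topical steroids are withheld in both arms, so their absence is not a vehicle-specific cause. More frequent artificial tears, the first listed response to worsening, does not lead to withdrawal. This objection stands: the imbalance is a possibility, not something that the plan predicts.

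**Is the harm hidden from the trial?** A reader might infer that the plan cannot detect drops that sting. It can. Section 3.2 has a separate primary tolerability endpoint, the VAS rating after dosing on Day 1 and at weeks 2 to 8, and 4.4.2 requests it from subjects who withdraw early. All adverse events are a secondary safety endpoint. This also stands, with two limits. The VAS endpoint is a change from the Day 1 post-dose rating, so steady discomfort would show in the ratings but not in the change. And neither measure compares how many had to stop, and for what reason.

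**Are the rates chosen to cancel?** The 15% row is. With similar worsening in both arms the distortion nearly vanishes, as the 3% row shows.

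**Is completion the safer endpoint?** It needs no attribution of cause. Burning, irritation and redness are both the likely drug effects in 1.5 and symptoms of dry eye in 1.1, so a reason-based primary endpoint could file drop irritation under worsening disease. This is a good argument against replacing completion. It is not an argument against reporting the causes beside it.

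**Conclusion.** The point holds for the primary safety comparison. The endpoint pools causes that can act in opposite directions between the arms, an arm comparison is planned on it, and no section analyses stopping by cause. If worsening is more frequent on vehicle, the comparison understates intolerance on drug.

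The size cannot be determined from the documents. With the assumed rates, the chance that the drug looks as good as or better than vehicle on completion runs from 8% to 56% as vehicle worsening goes from 3% to 15%. The result rests on 36 per arm, a 12-point intolerance difference, 3% worsening on drug and no other stops.

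The documents do not support saying that cancellation will occur, that the tolerability objective as a whole will be wrongly answered, or that the primary safety endpoint must be replaced. This is a cheap improvement that changes what may be concluded from equal completion.

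**What to change.** Keep all-cause completion as the primary safety endpoint. In 3.4 and 7.2, add:

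1. A key comparison by arm of the proportion who stop the drops for ocular discomfort or an adverse event, with a 95% CI for the difference.
2. A denominator of all randomised subjects who received a dose, including any replaced under 8.1, so that 7.3 does not drop stops before week 2.
3. Separate rows for stops for worsening dry eye or rescue, and for other stops.
4. Assignment of cause while masked, with a sensitivity analysis that counts ambiguous stops as intolerance.
5. A statement that equal completion will not be read as equal tolerability without this breakdown.

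**Cost.** Wording in two sections and one reason-for-withdrawal field. The field is needed because 8.4 and 8.5 cover only adverse events, and the diary in 5.5 gives reasons only for missed doses. The downside is that masked attribution is partly a judgement, which is why the sensitivity analysis is included. With about 36 per arm the interval will be wide. No clinical rule changes.
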